**Specific Aim 3:**

**To evaluate the extent to which a data-driven HOT management protocol can improve growth and respiratory outcomes.**

*We hypothesize that RHO utilization will not increase rates of respiratory-related re-hospitalizations and ED visits, and will not impair growth compared to standard oxygen management protocols.*

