## **4. Design and Methods**

### ***4a. Study Design***

We plan a prospective, multicenter, randomized trial of premature infants who require HOT. We will follow infants, beginning at the time of their first outpatient pediatric pulmonary appointment and continuing until 6 months from discontinuation of HOT. Duration of HOT therapy for each arm of the study will be documented by each site investigator. Questionnaires throughout the HOT managing process and after oxygen discontinuation will assess the impact of each HOT managing process on the parent quality of life. Growth assessments throughout of the HOT managing process and after oxygen discontinuation will track safety of both protocols. Similarly, assessment of health-care utilization (respiratory-related emergency department visits or rehospitalizations) at 6 months after discontinuation of HOT will track safety as well.

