#### **4.e. Definition of Primary and Secondary Outcomes/Endpoints**

Primary measures: (a) Total duration of home oxygen therapy (HOT) from the first outpatient pulmonary appointment to discontinuation of supplemental O2; and (b) Parent quality of life, assessed by differences in the post-weaning PedsQL baseline.

Secondary measures: (a) Number of rehospitalizations and emergency department visits from 1st clinic visit through 6 months after discontinuation of HOT; (b) Change in weight and weight-for-length z-score from 1st clinic visit to 6 months after discontinuation of HOT; and (c) For patients who will receive a sleep study, percent time below designated O2 saturation thresholds (<96%, <93%, and < 90%) will be calculated from both RHO and from the polysomnogram data. The number of desaturation events (defined as saturation drops below 90% for >10 seconds and > 20 seconds) will also be analyzed.

Duration of HOT was chosen as a primary outcome since it is the primary driver of caregiver emotional and financial health for families of infants on HOT. This outcome was driven by input from families themselves, through a process of including important stakeholders in the protocol development process. The PedsQL was chosen as an additional primary outcome because it is validated, accurate scale in which scores correlate with maternal psychiatric symptoms, poor child health, poor child adjustment, and increased child hospitalizations.

This protocol focuses on patient-centered outcomes that may demonstrate non-inferiority from a medical safety perspective, but may improve quality of life. While families place a priority on treatment strategies that optimize health, when there are multiple choices without a clear medically superior choice, then the impact of specific treatment choices on quality of life will help drive decision-making.

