**d. Statistical Power and Sample Considerations**

*Analyses for Aim 1:*

Aim 1: To evaluate the effects of a data-driven HOT management protocol on parent(s) quality of life.	Hypothesis 1.1: Parents of patients weaned from HOT using a data-driven management protocol will have improved quality of life compared to their status at time of NICU discharge compared to patients weaned using the current standard HOT management protocol.
--	--

For the impact of oxygen management protocol on the family's emotional health, we will use the PedsQL. We are performing these scales at the beginning of the outpatient HOT management process, to establish a baseline, and then will repeat these measures at the end of the HOT weaning process (6 months after discontinuation of HOT). We will test the association of oxygen management protocol with change in each measure using the Student's *t*-test to analyze the difference between intervention groups. Multivariate linear regression models will adjust for potential confounding variables, including parent and medical attributes.

Power calculation for hypothesis 1.1:

Power calculations are based on the primary analyses (t-test). A sample size of 130 will give 80% power, with 0.05 two-sided type I error rate, to detect a 20% absolute difference in emotional role limitation on the PedsQL, which we consider to be clinically significant.

*Analyses for Aim 2:*

Aim 2: To evaluate the impact of a data-driven HOT management protocol on duration of HOT.	Hypothesis 2.1: A data-driven HOT protocol will shorten duration of HOT therapy compared to the current standard HOT management protocol.
---	--

For the primary outcome, duration of HOT, the interval from date of first outpatient clinic visit/enrollment to discontinuation of HOT will be determined. Mean duration of HOT between the two groups will be compared.

Based on our experience weaning over 130 premature infants from O2, we expect the mean duration of HOT in our standard treatment group (clinic-based weaning) to be 144+/-66 days, and we anticipate that RHO weaning strategies will decrease the median duration by 25% (36 days) to 108 days. A total sample of 98 infants per group provides 97% power to detect this effect of the RHO strategy (two-tailed, alpha=0.05, see Table 2).

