**TABLE 2**

The power of detecting an effect of RHO on duration of HOT, indexed by the enrolled sample size and the difference in mean duration between the RHO and standard oxygen management group, assuming 85% completing all components of the study, a standard deviation of 66 days, and testing at the 2-tailed .05 level.

Difference in duration of HOT (days)	Enrolled n per group (double for total sample size)				
	33	44	53	60	98
30	45%	57%	65%	70%	89%
36	60%	73%	80%	85%	97%
49	85%	94%	97%	98%	>99%

*Analyses for Aim 3:*

Aim 3: To evaluate the extent to which a data-driven HOT managing protocol can improve growth and respiratory outcomes.	Hypothesis 3.1: Patients weaned from HOT using a data-driven protocol will have improved growth and decreased respiratory rehospitalizations compared to patients weaned using the current standard HOT weaning protocol.
--	--

The incidence of emergency department visits during HOT management process is estimated to be 30% in the RHO group and 40% in the standard weaning protocol. The two rates will be considered clinically noninferior if the difference was 10 percentage points or less (with a significance threshold of P=0.05 on a one-tailed test and 80% statistical power). On this basis, the number of patients required for each of the two treatment groups was calculated to be 65. With 98 patients per group the power increases to 93%.

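### The ED-visit safety comparison uses a window that closes relative to HOT discontinuation, so it favours RHO if RHO shortens HOT, and no exposure adjustment is stated

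*Combined protocol and SAP*

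**What the plan says.** Section 4e lists as a secondary measure the number of rehospitalizations and ED visits from the first "clinic visit through 6 months after discontinuation of HOT". That is a count, over a window whose length varies by infant.

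Section 5d, Analyses for Aim 3, plans on a percentage: "The incidence of emergency department visits during HOT management process is estimated to be 30% in the RHO group and 40% in the standard" arm. It then gives the criterion: "The two rates will be considered clinically noninferior if the difference was 10 percentage points or less", with a one-tailed 0.05 test. It states 65 per group for 80% power, and 93% power with 98 per group.

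Other passages bear on the window:
- Section 5d, Analyses for Aim 1, places the repeat PedsQL "at the end of the HOT weaning process (6 months after discontinuation of HOT"). If the same meaning were carried over to ED visits, the two windows would coincide. Nothing carries it over.
- Section 4a follows infants from the first pulmonary appointment, "continuing until 6 months from discontinuation of HOT", and says that health-care utilization assessed "at 6 months after discontinuation of HOT will track safety as well". It gives no start point for that assessment. In section 4f the final post-wean visit asks about events since oxygen was stopped.
- Section 5d, Analyses for Aim 2, expects a mean HOT duration of 144 days (SD 66) on standard management and that RHO will "decrease the median duration by 25% (36 days) to 108 days".
- Specific Aim 3 in the Abstract says that RHO "will not increase rates of respiratory-related re-hospitalizations and ED visits". The word suggests a time denominator, but none is defined, and section 5d uses the same word for percentages.

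Section 5c names no analysis for ED visits. Its gamma models are for oximetry, and the adjusted regression in section 5d is for PedsQL.

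**The concern.** HOT duration is what the intervention is meant to change. When the safety window closes at discontinuation, or a set time after it, the arm that stops oxygen sooner is watched for less time. With the same underlying ED hazard in both arms, a shorter span from the same starting point yields fewer expected events, whatever the shape of the hazard. The comparison therefore leans toward RHO to the extent that RHO succeeds on duration.

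This is the plan's only margin-based safety comparison, in a trial that aims to shorten HOT without compromising safety. A real increase in ED visits per day at risk could be partly hidden.

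**Working it through.** **Inputs.** From section 5d: ED incidence 30% (RHO) and 40% (standard), margin 10 points, one-sided alpha 0.05, 98 per group, HOT 144 v 108 days. From Table 2: 85% completion, so 0.85 × 98 ≈ 83 per arm. Assumed here: 6 months = 180 days; 108 days treated as a mean (the plan calls it a median); ED hazard constant unless stated.

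**1. The plan's own figures.** n = V(1.645 + 0.842)² / (0.10 + 0.10)².
- With V = 2 × 0.30 × 0.70 = 0.42, n = 64.9, i.e. 65. Power at 98 is Φ(0.20 × √(98/0.42) − 1.645) = 92.1%, close to the stated 93%.
- With the usual unpooled variance, 0.21 + 0.24 = 0.45, n = 70 and power at 98 is 90.4%.

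Both calculations count an assumed 10-point RHO benefit on top of the margin.

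**2. Observation time on the section 4e window.** Standard 144 + 180 = 324 days; RHO 108 + 180 = 288 days. The ratio is 288/324 = 0.889, so RHO is observed 11% less. At equal constant daily rates the expected RHO count is 11% lower. A daily rate 12.5% higher under RHO (324/288 = 1.125) would give equal mean counts.

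**3. Binary illustration, RHO truly at the margin.** Let p be the control risk over 324 days and p + 0.10 the RHO risk over the same 324 days. Observed RHO risk = 1 − (1 − p − 0.10)^0.889. P(declare non-inferior) = Φ((0.10 − observed difference)/SE − 1.645), with SE unpooled.
- p = 40%: observed RHO risk 1 − 0.50^0.889 = 46.0%, so bias is 4.0 points. With 98 per arm SE = 0.0706 and the probability is 14.1%; with 83 per arm it is 13.1%.
- 40% taken as the 144-day risk instead: p = 1 − 0.60^(324/144) = 68.3% and observed RHO risk is 74.3%. Bias is again 4.0 points, with probability 15.3% (98) or 14.2% (83).
- Nominal error is 5%.

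**4. Sensitivity.**
- Weibull shapes k = 0.5 to 1.5 (exponent 0.889^k, both calibrations): about 8% to 21% across 83-98 per arm.
- HOT only 15 days shorter (309/324): bias 1.6 points, probability about 8%.
- Equal durations: bias 0, error 5%.
- If the window ended at discontinuation (108/144 = 0.75): observed RHO risk 1 − 0.50^0.75 = 40.5%, bias 9.5 points, probability 38% (98) or 34% (83).

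**5. What a fixed window does to power.** With equal 40% risks V = 0.48, and power is Φ(0.10 × √(n/0.48) − 1.645): 41% at 98 and 37% at 83. About 297 per arm would be needed for 80%.

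**6. Coverage of a fixed window.** Follow-up is HOT duration plus 6 months, so every infant who completes it is observed to at least day 180. With assumed gamma durations (standard mean 144, SD 66; RHO 0.75 times that), about 26% of standard and 9% of RHO infants are still on HOT at day 180. Mean post-wean time within the 180 days is about 50 and 75 days. By contrast, only about 79% and 59% of completers would be followed to day 270.

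**The case against.** Several points on the other side have force.

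- **The windows may not differ.** The Aim 1 wording in section 5d could make the weaning process run to 6 months after discontinuation. That stands as a possibility, but the phrase concerns PedsQL. Even if it applied, the shared window would still close at a time tied to discontinuation.
- **An equal-length interval exists.** Sections 4a and 4f describe assessment at 6 months after discontinuation, or since it. That interval is equally long in both arms and is when harm from early weaning could appear. It is useful, but it is not the stated endpoint: section 4e starts at the first visit.
- **Section 4e should govern.** It defines the endpoint, and the Aim 3 text is a planning paragraph. This is the more natural reading. A reader might infer from section 5d that false non-inferiority is near 38%. That needs the HOT-only window to govern, which the documents do not establish.
- **The size rests on assumptions.** The documents give no ED hazard and do not define a binary equal-window endpoint. Section 4e defines a count, for which the assumption-light result is 11% less observation time, and only under the full hypothesised effect. This also stands.

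None of these points supplies an exposure adjustment.

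**Conclusion.** The point holds, conditionally and at moderate size. On either the section 4e or the section 5d window, observation ends at a time set by a primary outcome, and the plan states no common window, offset or exposure adjustment. If RHO shortens HOT by the hypothesised 36 days, the section 4e comparison tilts toward RHO. The direction does not depend on the shape of the hazard; the bias and error rates in the working do, and they are illustrations.

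Two stronger readings should be resisted. The documents do not show that the comparison is biased whatever happens, since equal durations leave none. Nor do they show that the two windows definitely conflict; they show that the windows read differently and are never reconciled. ED visits are a secondary outcome, so this should be fixed but does not undermine the primary analyses.

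**What to change.** - Reconcile section 4e with the Aim 3 text in section 5d: one window and one measure for the non-inferiority test.
- State whether the event is any ED visit or a respiratory-related one. The section 4e definition has no qualifier; Specific Aim 3, section 4a, the rationale closing section 4e and the final-visit text in section 4f say respiratory-related.
- Define the non-inferiority endpoint as the proportion with an event over one fixed interval from randomisation, identical in both arms and covered by follow-up for every completer, for example 180 days.
- Analyse the section 4e counts over full follow-up as rates (negative binomial, log follow-up time as offset). Note that this removes the bias fully only if the hazard is roughly constant: identical Weibull hazards give a rate ratio of 0.889^(k−1), i.e. 1.06 at k = 0.5 and 0.94 at k = 1.5.
- Report events in the equal 6 months after discontinuation as supportive.
- If a longer fixed window is preferred, use Kaplan-Meier risks with a sensitivity analysis for censoring that depends on HOT duration.
- Re-derive the planning proportions for the chosen window and restate the power.

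**Cost.** No new visits or data: section 4f already records these events to 6 months post-wean. A 180-day window captures less post-wean time than full follow-up. The stated power becomes less favourable, about 41% at 98 per arm or 37% at 83 if both risks are 40%, mainly because the assumed 10-point RHO benefit is removed and not because of the window.

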Although our primary outcomes focus on quality of life, the secondary outcomes were chosen to confirm that weaning strategies (that likely improve quality of life) are not less safe. Assessment of short-term outcomes after discontinuation of therapies may miss significant later morbidities. We therefore included clinically relevant secondary outcomes at 6 months post discontinuation of O2 to assess the safety of the weaning strategies. Inadequate O2 supplementation has been associated with poor somatic growth, so growth parameters are an important outcome to confirm long-term safety of all studied weaning protocols. Higher O2 target saturations, with subsequent increased exposure to supplemental O2, have been linked to increased numbers of respiratory exacerbations. We therefore are also including rates of respiratory-related emergency department visits and rehospitalizations as additional secondary outcomes.

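### The safety outcome is defined as a number of visits, but the only stated test compares the percentage with an ED visit, so the formal non-inferiority result cannot register repeat visits

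*Combined protocol and SAP*

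**What the plan says.** Section 4.e lists secondary measure (a) as "Number of rehospitalizations and emergency department visits from" the first "clinic visit through 6 months after discontinuation of HOT". The rationale later in that section calls the same outcome "rates of respiratory-related emergency department visits and rehospitalizations as additional secondary outcomes". Section 4f (All Visits, Adverse events) has each event sought by interview throughout the study and after weaning, verified against records, and entered on the Adverse Event form.

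The only decision rule is in section 5d, Analyses for Aim 3. Its starting figures are "The incidence of emergency department visits during HOT management process is estimated to be 30% in the RHO group", against 40% for standard management. The criterion is "The two rates will be considered clinically noninferior if the difference was 10 percentage points or less", one-tailed at 0.05. The paragraph gives 65 per group for 80% power, and 93% power at 98 per group.

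Section 5c names an independent-sample test and a chi-square test for baseline characteristics and duration of oxygen. It names a GEE gamma regression only for comparing sleep-study and home oximetry. Neither 5c nor 5d gives a model or test for the number of ED visits, or any test for rehospitalizations, although Hypothesis 3.1 names rehospitalizations.

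**The concern.** The outcome is defined on one scale and tested on another. A percentage per arm with a percentage-point margin is a yes/no outcome per infant, so second and later visits carry no weight. The tested quantity also drops rehospitalizations and covers only the period on oxygen, whereas the definition runs 6 months past it.

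This matters because section 4.e says the secondary outcomes are there to confirm that the weaning strategies are not less safe. If RHO sent the same share of infants to the ED, or a smaller share, but brought them back more often, the stated rule would still report non-inferiority. The plan has no other between-arm analysis that would show the excess.

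**Working it through.** **1. Is the stated test on proportions?** Inputs from 5d: 40% and 30%, margin 0.10, one-sided alpha 0.05, power 80%. RHO is assumed 10 points better, so the distance from the margin is 0.10 + 0.10 = 0.20.

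- Binomial variance at 30% in both arms: n = 2 × 0.30 × 0.70 × (1.645 + 0.842)² / 0.20² = 64.9, so 65, as stated. Power at 98 is 92.1%, close to the stated 93%.
- Variance at the stated 40% and 30%: n = (0.24 + 0.21) × (1.645 + 0.842)² / 0.20² = 69.6, so 70. Power at 98 is 90.4%, the reference used below.

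The plan's 65 comes out of a binomial formula, which supports the yes/no reading.

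**2. Can repeat visits change the verdict?** Assumptions (the documents give no count distribution): 98 per group; 30% (RHO) and 40% (standard) have at least one visit; standard-arm visitors average 1.5 visits; visits per visitor are one plus a Poisson number. 20,000 simulated trials per row.

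| Visits per RHO visitor | Total visits, RHO / standard | Yes/no rule declares non-inferiority | One-sided comparison of mean counts shows RHO worse |
|---|---|---|---|
| 1.5 | 0.30 × 1.5 / (0.40 × 1.5) = 0.75 | 90% | under 1% |
| 2 | 0.30 × 2 / 0.60 = 1.0 | 91% | 4% |
| 3 | 0.30 × 3 / 0.60 = 1.5 | 90% | 49% |
| 4 | 0.30 × 4 / 0.60 = 2.0 | 90% | 87% |

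The third column does not move, because the rule uses only whether a visit occurred. The last column depends on the assumed spread: with geometric visits per visitor and the same means, its last two entries fall to 38% and 73%.

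**3. Does the yes/no scale lose power?** Non-inferiority power at 98 per group, one-sided 0.05, is Φ[(ln margin − ln rate ratio)/SE − 1.645]; the yes/no test has 90.4%. For negative binomial counts with means m₁, m₂ and dispersion k, SE = √[(1/m₁ + 1/m₂ + 2k)/98].

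- (a) Hold the chance of any visit at 30% and 40%, and convert 50% versus 40% to a rate-ratio margin. At k = 0 the means are 0.357 and 0.511, the rate ratio is 0.698, the margin is 1.357 and SE = 0.220, giving 91.5%. At k = 0.5, 1 and 2: 94.5%, 96.6%, 98.9%. The count looks better, but by k = 2 the assumed rate ratio has moved to 0.585 and the tolerated one to 1.687, so effect and margin both grow with k.
- (b) Hold means and margin at the k = 0 values and raise k to 0.5, 1, 2, 4: 86.4%, 81.2%, 71.9%, 57.8%. The count is weaker.
- (c) Give both arms the same geometric mean r of visits per visitor: rate ratio 0.30/0.40 = 0.75, margin 0.50/0.40 = 1.25. The squared coefficient of variation in an arm is (2 − 1/r)/p − 1. At r = 1.5: SE = √[(2.333 + 3.444)/98] = 0.243, giving 67.7%. At r = 2 and 3: 61.9% and 56.9%. The count is weaker. At r = 1, where the two data sets are identical, power is 82.6%, so part of the gap comes from the ratio-scale margin alone.

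A two-sided test of difference, which the plan does not state, splits the same way: 31% for yes/no, against 37% to 52% under (a) and 17% to 22% under (c).

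**The case against.** Section 4.e does not say per infant, and its rationale speaks of rates. The 5d paragraph is about sample size and never spells out that it counts infants with a visit. A proportion with a margin is a legitimate choice for a secondary outcome. These points soften the textual case but leave it standing: a percentage incidence, a percentage-point margin and a binomial sample size fit only a yes/no outcome, and no analysis of the number is offered.

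A reader might go further and infer that the yes/no scale costs power. The documents do not support that. They give no mean count or dispersion, and step 3 shows a gain of about 1 to 9 points under one set of assumptions and a loss of up to about 33 points under others.

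A reader might also infer that repeat-visit harm cannot count against RHO at all. That is too strong. All adverse and serious adverse events go to the DSMB every 6 months (section 4h), and section 5f convenes the DSMB, and can stop the study, on respiratory hospitalizations in an arm. Those triggers do not cover ED visits, though, and they govern conduct rather than the final comparison. The gap in the formal test remains.

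**Conclusion.** The point holds in limited form. Measure (a) is defined as a number of ED visits and rehospitalizations through 6 months after oxygen ends; the only stated rule tests the percentage with an ED visit during oxygen management; the count and rehospitalizations have no analysis. The blindness of the rule to repeat visits follows from its form and needs no assumption. The illustration does: about 90% declared non-inferior at 1.5 or 2 times the total visits rests on 30% and 40% having any visit. The claim extends neither to lost power nor to safety oversight during the trial. This is a cheap improvement to a secondary analysis, worth making because that analysis carries the trial's safety question.

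**What to change.** In section 5d, Aim 3:

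- Keep the 10-percentage-point comparison.
- Add an analysis of measure (a) as defined: ED visits per infant and, separately, rehospitalizations per infant, by negative binomial regression with log follow-up time as offset and robust standard errors. Report each RHO/standard rate ratio with its confidence interval beside the existing test.
- State the window for each analysis, and whether events are all-cause or respiratory-related. The offset matters because the plan expects oxygen to fall from 144 to 108 days. At a constant and equal daily visit rate, 40% over 144 days becomes 1 − 0.60^(108/144) = 31.8% over 108 days, so shorter exposure alone could produce most of the assumed 10-point advantage.
- Qualify any non-inferiority statement by the rate-ratio interval. An interval that merely fails to show excess visits is not proof of safety; a formal second criterion would need its own prespecified rate-ratio margin.

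The cost is a few lines of text and one more model form, fitted to events already collected. The downside is an estimate sensitive to a few infants with many visits, which the robust standard errors only partly address.

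### Aim 3 non-inferiority: the stated inputs give about 70 per group and about 90% power at 98, not 65 and 93%, and that power assumes RHO is 10 points better

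*Combined protocol and SAP*

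**What the plan says.** All the inputs are in Section 5d (Statistical Power and Sample Considerations), Analyses for Aim 3.

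- Rates: "The incidence of emergency department visits during HOT management process is estimated to be 30% in the RHO group and 40" per cent in the standard arm.
- Margin: "The two rates will be considered clinically noninferior if the difference was 10 percentage points or less". The test is one-tailed at 0.05 with 80% power.
- Result: the number per group "was calculated to be 65. With 98 patients per group the power increases to 93" per cent.

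No formula is named and no dropout allowance is attached to this calculation.

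Three other statements bear on what the power figure means.

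- The hypotheses differ. Hypothesis 3.1, directly above the calculation, says that infants weaned by the data-driven protocol "will have improved growth and decreased respiratory rehospitalizations compared to patients weaned using the current standard HOT weaning protocol". Specific Aim 3 in the Abstract instead says that "RHO utilization will not increase rates of respiratory-related re-hospitalizations and ED visits".
- Section 4e gives the purpose: "the secondary outcomes were chosen to confirm that weaning strategies (that likely improve quality of life) are not less safe".
- Section 4e also defines secondary measure (a) as the number of rehospitalizations and ED visits from the first "clinic visit through 6 months after discontinuation of HOT". The powered event is ED visits during HOT management only.

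**The concern.** The rates, margin, alpha and target power are all printed, so the sample size and the power at 98 can be checked directly. Both fail the check, and both err on the optimistic side: the required number is too small and the power too high.

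This is the plan's only power statement for a secondary outcome, and Section 4e gives those outcomes the job of confirming safety. A reader who takes 93% as assurance for a no-increase claim would not see two things. The figure is about 3 points too high on its own inputs. It also rests on RHO lowering the ED-visit rate from 40% to 30%. If the two strategies are simply equal, the trial would more likely than not fail to show non-inferiority, and that failure would say little by itself.

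**Working it through.** **Inputs** (Section 5d, Aim 3): RHO rate 0.30, standard rate 0.40, margin 0.10, one-sided alpha 0.05 (z = 1.645), power 80% (z = 0.842). Allocation is equal (98 per group; block randomization in Section 4f). The plan does not give the direction of the margin. I read it as RHO minus standard below +10 points, because an absolute difference would put the assumed 10-point gap on the margin itself.

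**Distance and variance.** Distance from the assumed truth to the margin: 0.10 − (0.30 − 0.40) = 0.20. Unpooled variance sum: 0.30×0.70 + 0.40×0.60 = 0.21 + 0.24 = 0.45.

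**Attempt to reproduce 65.** n = (1.645 + 0.842)² × 0.45 / 0.20² = 69.6, so 70 per group. The plan's 65 is not reproduced.

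**Attempt to reproduce 93%.** Power = Φ(0.20 × √(n/0.45) − 1.645).

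- n = 65: Φ(2.404 − 1.645) = 77.6%.
- n = 98: Φ(2.952 − 1.645) = 90.4%.
- n needed for 93%: (1.645 + 1.476)² × 0.45 / 0.04 = 109.6, so 110.

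**Other methods with the same rates.**

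| Method | n for 80% | Power at 65 | Power at 98 |
|---|---|---|---|
| Unpooled | 69.6 | 77.6% | 90.4% |
| Farrington-Manning | 69.9 | 77.4% | 90.3% |
| Pooled null variance | 70.1 | 77.3% | 90.3% |
| Exact binomial power of the Wald test | 79.7% power at 70 | 77.4% | 90.1% |

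Stricter choices move further from 65: a continuity correction gives 80 per group, and one-sided 0.025 gives 89. Nothing that keeps 30% and 40% gives 65 or 93%.

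**Sensitivity to the assumed RHO advantage** (98 per group, same margin and alpha):

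- 35% vs 40%, distance 0.15: Φ(0.15/√(0.4675/98) − 1.645) = 70%.
- Equal rates, Φ(0.10/√(2p(1−p)/98) − 1.645): 41% at 40/40 and 45% at 30/30 (exact 41% and 46%).
- With 40% in the standard arm, RHO must be about 7 points better to reach 80% power.
- At equal rates, 80% power would need 260 (30/30) to 297 (40/40) per group.

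**Completion.** Table 2, on HOT duration, is computed "assuming 85% completing all components of the study". Nothing says this applies to Aim 3. If it is assumed to, 0.85 × 98 = 83.3, or 83 per group. Power is then about 86% at 30/40, and 37% (40/40) to 41% (30/30) at equal rates.

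**The case against.** The best counter-argument is that little follows from the error. The figure of 65 is not used, since 98 per group are planned. What remains is 93% against about 90% for a secondary outcome. That is right, and it limits the weight of the point.

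A second argument is that an input, not an output, may be misprinted. Variance taken at 30% in both arms gives 64.9 per group, but 92.1% at 98. A 20% vs 40% comparison gives 93.1% at 98 with unpooled variance, and 64.9 only if the variance is switched to the average rate. A standard one-sided test of those rates gives 64 and 92.6%. These come close, but each departs from the printed rates and none gives both 65 and 93% from one formula. The origin is unknown, which is why the method should be named.

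Third, the 30/40 assumption is printed beside the power statement and agrees with Hypothesis 3.1. A no-increase aim is also compatible with a true decrease. So the equal-rates power is not evidence of an error and not the trial's actual power. It remains useful because the Abstract and Section 4e frame the aim as no harm.

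Fourth, Section 4f has ED visits collected by interview and checked against records, so failing to complete every study component need not mean a missing ED outcome. That stands, and the 83-per-group figures are therefore conditional only. The hypothesis and endpoint mismatches are wording points and do not alter the recomputation.

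**Conclusion.** The figures are wrong as written. On the printed inputs, with the margin read as RHO no more than 10 points worse, 80% power needs 70 per group (70 or 71 by formula without continuity correction). Power at 98 is about 90%, so the stated power is about 3 points too high and the stated size about 5 infants per group too small. The error should be corrected, but it changes no design decision.

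The dependence on a 10-point RHO advantage is a matter of disclosure: the equal-rates figure of about 41% to 45% at 98 per group should be visible to the reader. Two wording conflicts need reconciling so that it is clear what the power refers to. Hypothesis 3.1 is worded as superiority above a non-inferiority calculation, and the powered event covers a shorter window and fewer event types than the secondary outcome in Section 4e.

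**What to change.** In Section 5d, Analyses for Aim 3:

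1. Replace 65 with 70 and 93% with about 90%. Name the formula and state the direction of the margin. If a different input was intended, correct that input and show that the outputs follow from it.
2. Say that this power assumes RHO is 10 points better, and give the equal-rates figure (about 41% to 45% at 98 per group).
3. If 85% completion is meant to apply here, label it as an assumption and give about 86% (37% to 41% at equal rates) at 83 per group. Otherwise leave it out.
4. Reconcile Hypothesis 3.1 with the no-increase hypothesis in the Abstract.
5. State that the figures are for ED visits during HOT management, not for the Section 4e outcome that also counts rehospitalizations and runs to 6 months after discontinuation.

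The cost is a few sentences of text. Stated power falls by about 3 points; enrolment and design stay as they are.
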